3.2. Study duration and milestones

The study will last 24 months from the first patient enrolled, for patient recruitment. Each subject will participate for a maximum of 24 months.

4. Study population

4.1. Recruitment

Suitable subjects will be identified from patients referred to the IBD Unit of the Digestive Disease Center (CEMAD) of Fondazione Policlinico Universitario Agostino Gemelli IRCCS in Rome Italy and to all others IBD Unit of all centres involves. Based on the number of patients that are referred to the clinics, we estimate that 30 patients per month, time for recruitment is 24 months. The potential study participants will receive oral and written information of the study. Patients that agree to participate in the study will be asked to sign a written informed consent according to GCP.

4.2. Inclusion criteria

The participants must fulfill the following criteria for participating in the study:

1. Age of at least 18 years.
2. Patients with a previous diagnosis of CD at least 3 months before baseline.
3. Patients who have failed at least one advanced (biological or small molecule) therapy for CD and who have experienced failure to at least one mechanism of action (failure is defined as primary failure, secondary failure, or intolerance).
4. Patients, with any grade of clinical or endoscopic disease activity who have started a therapy with risankizumab for CD based on clinical practice indication (primary loss of response, secondary loss of response, intolerance to the previous drug).
5. Written informed consent certifying the willingness of the subject to participate to the study.

4.3. Exclusion criteria

1. Age < 18 years.
2. Patients with diagnosis of indeterminate IBD.
3. Patients naive to advanced (biological or small molecule) therapy for IBD.
4. Refusal to sign written informed consent certifying the willingness of the subject to participate to the study.

4.4. Sample size evaluation and statistical analysis

Based on the real-life study design and on the primary endpoint, which foresees a descriptive evaluation of remission rates according to each therapy line considered, we present diverse scenarios of potential sample size (from 50 till 300 by 25), and related confidence intervals in order to detect a CPDR at 12 months of 50-55 and 60% according to the evidence available from the current literature on the drugs under investigation. All scenarios are assessed according to a single group study design with a two-sided 95% confidence interval for a single proportion. A table with all potential scenarios will be provided as attachment.

As an example, such single-group design to obtain a two-sided 95% confidence interval for a single proportion, assuming a sample proportion of 0.5, with a sample size of 50, would produce a confidence

interval width of 0.28945, i.e., 0.5 ± 0.145 . The confidence interval widths were computed using PASS 2022, version 22.0.4 [29].

Based on the data available to the participating centers (for the retrospective phase) and the recruitment capabilities of the centers during the enrollment period, we expect to enroll 200 subjects with Crohn disease in this retrospective study.

The sample will be described in its clinical and demographic characteristics by descriptive statistics techniques. In depth, qualitative data will be expressed as absolute and relative percentage frequency, whilst quantitative variables either by mean and standard deviation (SD) or median and interquartile range (IQR), as appropriate. To verify the Gaussian distribution of quantitative variables, the Shapiro-Wilk test will be applied. Eventual missing values (if <5%) will be treated by *imputeR* package, using multiple imputation with Lasso Regression methods centered on the mean for quantitative data, whilst classification trees for imputation by “*rpartC*” function, centered on the mode, i.e. most represented class object, will be applied on qualitative data [30]. The sample will be described in its clinical and demographic characteristics by descriptive statistics techniques. In depth, qualitative data will be expressed as absolute and relative percentage frequency, whilst quantitative variables either by mean and standard deviation (SD) or median and interquartile range (IQR), as appropriate. To verify the Gaussian distribution of quantitative variables, the Shapiro-Wilk test will be applied. Eventual missing values (if <5%) will be treated by *imputeR* package, using multiple imputation with Lasso Regression methods centered on the mean for quantitative data, whilst classification trees for imputation by “*rpartC*” function, centered on the mode, i.e., most represented class object, will be applied on qualitative data [30].

Between-group differences at baseline will be assessed by either the Chi-squared or the Fisher-Freeman-Halton's exact test for qualitative variables, whilst with either one-way ANOVA or non-parametric Kruskal Wallis will be applied to quantitative data. Pairwise comparisons will be performed by either Student's t test or Mann-Whitney U test, as appropriate, with “False Discovery rate” correction for multiple comparisons. AEs and SAEs will be assessed by descriptive statistics and compared among the different lines with the aforementioned inferential tests.

The evaluation of the difference in terms of CPDR at 12 months and 24 months, respectively, according to the different biological sequential therapies at II and III lines will be evaluated by Kaplan-Meier survival analysis. In particular, the log-rank test will be applied and appropriate cumulative incidence curves will be drawn. The analysis will be performed using the R packages “*ggplot2*” and “*survminer*” [31,32].

Potential predictors of CPDR will be assessed by Cox regression models. In detail, the potential predictors of the outcome will be evaluated by means of ordinary proportional hazards Cox regression models, and the Hazard Ratios (HR) and the 95% confidence intervals (CIs) will be reported. The proportionality of the hazard functions will be evaluated by visual inspection of the hazards and Schoenfeld residual plots. In case of doubtful proportionality, Cox weighted regression models will be

fitted. The analysis will be performed with "*survival*" and "*coxphw*" R packages [33-37]. Whether possible due to the different sample sizes of each therapeutic line and sequential strategy, to evaluate the combined effects between drug and line of administration, multivariable interaction models will be fitted, one per each predictor, and the interaction hazard ratios (IHR) reported. In summary, the coefficients of the main effects (in exponential terms) will be interpreted as HRs of the outcome by considering a unit increase of the predictor in the reference category (first line) (HR_{predictor}) as for quantitative predictors, whilst as increase in the hazard of the outcome occurring, as compared with the (arbitrarily) chosen reference group for qualitative data. The interaction parameters (IHR) will be interpreted as difference (in HR terms) of variations of the predictors among the different lines (first line as reference category).

5. Study procedures

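### Section 4.4 imputes only below 5% missing, calls a mean- or mode-centred fill multiple imputation, and offers nothing at 5% or more, where bias can be large

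*Protocol*

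**What the plan says.** Protocol Section 4.4 gives its missing-data rule in a paragraph that is printed twice. The opening condition is "Eventual missing values (if <5%) will be treated by" a named R package. The method follows: "using multiple imputation with Lasso Regression methods centered on the mean for quantitative data, whilst classification trees for imputation by" a tree function, with the qualitative fill "centered on the mode, i.e. most represented class object, will be applied on qualitative data".

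The text does not say whether the 5% is counted per variable, per patient or over the whole data set. It gives no handling for 5% or more, and mentions neither a number of imputed data sets nor pooling. It does not say whether CPDR is inside or outside the rule.

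The same section plans the study around an interval for one proportion, "in order to detect a CPDR at 12 months of 50-55 and 60" per cent, and states that "we expect to enroll 200 subjects with Crohn disease in this retrospective study".

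Section 2.1 builds 12-month CPDR from abdominal pain, stool consistency, three months of steroid history, and at least one of calprotectin, endoscopy or imaging. It does not say how a patient without evaluable data is classified. Section 5.1 takes the data from the centres' electronic archives.

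**The concern.** There are three weaknesses in the rule as written.

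- **The threshold points the wrong way.** Imputation is permitted where it can hardly change the answer, and no remedy is given where it could.
- **The label does not match the method.** Multiple imputation needs several plausible values per gap and a pooled variance. A fill centred on the mean or mode, with no repeated draws described, treats guessed values as observed. Used for covariates, it would also feed the Cox predictor models.
- **The primary outcome is not protected.** CPDR is a qualitative variable, and nothing exempts it from a modal fill.

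The main result is a single descriptive proportion from archive data. If outcome data are missing in more than a few patients, their handling can move that proportion by more than its planned precision.

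**Working it through.** **Inputs.** From Section 4.4: N = 200; expected CPDR 50%, 55% or 60%; two-sided 95% interval; imputation only below 5%. The protocol gives no expected missing rate, so 10%, 20% and 30% below are assumptions.

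**1. The plan's own figure.** Section 4.4 gives, "assuming a sample proportion of 0.5, with a sample size of 50", an "interval width of 0.28945, i.e., 0.5 ± 0.145". The exact (Clopper-Pearson) interval for 25/50 is 0.35527 to 0.64473, width 0.28945. The figure reproduces, so exact intervals are used below.

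**2. Planned precision at N = 200.** For 110/200 = 55% the interval is 47.8% to 62.0%, width 0.142, or a half-width of about 7 points.

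**3. Below the threshold.** Under 5% of 200 means at most 9 patients (4.5%), leaving 191 observed. Suppose all 9 receive the overall modal class:

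- Observed 55%: (0.55 × 191 + 9)/200 = 114.05/200 = 57.0%, up 2.0 points.
- Observed 60%: (0.60 × 191 + 9)/200 = 123.6/200 = 61.8%, up 1.8 points.
- Observed 45%: (0.45 × 191)/200 = 85.95/200 = 43.0%, down 2.0 points, because the mode is now non-remission.
- Observed 50%: there is no single mode.

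Treating the 9 as observed also shortens the interval, by a factor of roughly √(191/200) = 0.977, about 2%.

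**4. At 5% or more, with 55% observed.** Let m be the number missing and x = 0.55 × (200 − m). Complete-case is x/(200 − m); the lower bound, all missing not in CPDR, is x/200; the upper bound, all missing in CPDR, is (x + m)/200.

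| Missing (assumed) | x / observed | Complete-case 95% CI | Lower bound | Upper bound |
|---|---|---|---|---|
| 10% (20) | 99/180 | 47.4–62.4% | 49.5% | 59.5% |
| 20% (40) | 88/160 | 46.9–62.9% | 44.0% | 64.0% |
| 30% (60) | 77/140 | 46.4–63.4% | 38.5% | 68.5% |

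The bounds concern the 200 patients themselves, before any sampling error. At 10% they lie inside the complete-case interval. At 20% and 30% they extend beyond it on both sides. At 20% the lower bound is 55 − 44 = 11 points below the complete-case figure, more than the 7-point half-width.

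**5. Interval width.** Complete-case 88/160 has width 0.159. Counting the 40 missing as not in CPDR, 88/200, has width 0.142. Dropping patients widens the interval; the danger is that it sits in the wrong place.

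**The case against.** The strongest reply is that Section 4.4 is simply silent at 5% or more, and that a statistical analysis plan, not shown here, may supply the rule. That is fair as far as the silence goes: complete-case analysis is nowhere named and is only the implied default. It does not answer the rest, because the threshold and the mislabelled method are written into the protocol.

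A second reply is that the rule may be meant only for sample characteristics. Its paragraph opens with the description of the sample, and the CPDR analyses come later without mention of imputation. This stands as a doubt about scope. The wording is nevertheless general and exempts no variable.

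A third reply is that Section 3.1 admits only patients with the required data available, and that any one of three objective markers is enough, so little may be missing. That may lower the count, but it does so by selecting on completeness, a separate risk.

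A reader might go further and infer that both branches push the remission rate up and make its interval too narrow. The documents do not support this. Remission is the modal class only above 50%, and a classification tree predicts within nodes and need not return the overall mode. Complete-case analysis lengthens the interval. Nor does the protocol say why data would be missing, so the idea that the missing patients are mostly those who stopped treatment is an assumption.

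**Conclusion.** The point holds in limited form. As written, Section 4.4 confines imputation to less than 5% missing, leaves 5% or more without a stated method, and gives the name multiple imputation to a fill that carries no imputation uncertainty.

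Below the threshold the harm to the primary proportion is minor: about 2 points at most at N = 200, in either direction, and only if CPDR falls under the rule and every gap takes the overall mode. Above it, the possible error equals the missing fraction: a 20-point range, 44% to 64%, if 20% were missing and 55% of the observed were in CPDR. That range rests on an assumed missing rate and on extreme allocations of the missing patients. It shows what the plan leaves open and does not predict a bias of that size or direction.

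This should be corrected before results are seen. It does not invalidate the design.

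**What to change.** Rewrite the missing-data paragraph of Section 4.4, keeping one copy, as follows:

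- Remove the 5% threshold.
- State that CPDR and its components are not filled with the modal class.
- Report the primary proportion over all included patients, counting a missing or non-evaluable 12-month CPDR as not in CPDR.
- Give two sensitivity analyses: complete-case, and proper multiple imputation with several data sets pooled by Rubin's rules.
- Use the same multiple imputation for missing covariates in the predictor models, whatever the percentage missing.

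The cost is wording and a little more programming; no new data are needed. The reported remission rate will be somewhat less favourable, since counting missing as not in CPDR gives the lower bound; the sensitivity analyses show how much depends on that choice. The change does not reach patients kept out by the data-availability condition in Section 3.1, which is a separate question.

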4. To evaluate the percentage of patients achieving endoscopic remission of CD (defined as SES-CD ≤ 4 and at least a 2-point reduction vs baseline and no subscore > 1 in any individual variable) after 3 months, 6 months, 12 months and 24 months of risankizumab.
5. To evaluate the percentage of patients showing endoscopic response of CD (defined as a greater than 50% decrease in SES-CD from baseline (or for isolated ileal disease and a baseline SES-CD of 4, at least a 2-point reduction from baseline) after 3 months, 6 months, 12 months and 24 months of risankizumab.

6. To evaluate the percentage of patients achieving the steroid-free “deep remission” of CD, defined as the combination of clinical remission and endoscopic remission according to the above mentioned criteria (PMID: 26303131) after 6 months, 12 months and 24 months of risankizumab.
7. To evaluate the percentage of CD patients achieving transmural healing at CT-scan or MRI enterography or at intestinal ultrasound (defined as a BWT \leq 3 and normal parietal contrast enhancement or color Doppler signal (CDS) or absence of hyperemia) after 3 months, 6 months, 12 months and 24 months of risankizumab.
8. To evaluate the percentage of patients showing response of CD at radiological exams, including CT-scan or MRI enterography and intestinal ultrasound (defined as a decrease in BWT by 25% from baseline or 2.0 mm, or greater than 1.0 mm with a decrease in parietal contrast enhancement or in CDS assessed by the modified Limberg score of one grade) after 3 months, 6 months, 12 months and 24 months of risankizumab.
9. To assess the variation of C-reactive protein (CRP) after 3 months, 6 months, 12 months and 24 months of treatment with risankizumab in CD patients.
10. To identify clinical, endoscopic or radiologic predictors of deep remission in CD at 12 months and 24 months.
11. To evaluate the percentage of patients achieving control of extraintestinal manifestation at 3 months, 6 months, 12 months and 24 months.
12. To compare the efficacy of risankizumab, as assessed according to the primary endpoint of the study, when used as second, third or fourth line of biological treatment.
13. To assess the safety of risankizumab during the entire study period.

2. Study endpoints

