12. Comparison between the efficacy of risankizumab, as assessed according to the primary endpoint of the study, when used as second, third or fourth line of biological treatment.
13. Assessment of the safety of risankizumab during the entire study period.

3. Study design and investigational plan

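### The between-line tests for AEs and SAEs take no account of observation time, so a systematic difference in follow-up between treatment lines could create or mask a safety difference

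*Protocol*

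**What the plan says.** The safety aim (section 2, secondary aim 13) is "To assess the safety of risankizumab during the entire study period", and endpoint 13 in section 2.2 repeats it: "Assessment of the safety of risankizumab during the entire study period". Section 3.2 adds that "Each subject will participate for a maximum of 24 months". The protocol sets no minimum follow-up and no common risk window for adverse events.

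The analysis is fixed in section 4.4: "AEs and SAEs will be assessed by descriptive statistics and compared among the different lines with the aforementioned inferential tests". The tests named just before that sentence are:

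- for categorical variables: "Between-group differences at baseline will be assessed by either the Chi-squared or the Fisher-Freeman-Halton's exact test for qualitative variables";
- for quantitative variables: "one-way ANOVA or non-parametric Kruskal Wallis will be applied to quantitative data";
- for pairs of groups: "Pairwise comparisons will be performed by either Student's t test or Mann-Whitney U test, as appropriate", with a false-discovery-rate correction.

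On description, the section says that "qualitative data will be expressed as absolute and relative percentage frequency". It names Kaplan-Meier curves, the log-rank test and Cox models for clinical-practice deep remission (CPDR) and its predictors, but not for safety.

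**The concern.** The listed tests are introduced for baseline characteristics, where length of follow-up plays no part. They are then carried over to an outcome that accumulates with follow-up.

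A chi-squared or exact test would compare the share of patients with an event. ANOVA, Kruskal-Wallis, t or Mann-Whitney tests would compare event counts per patient. Both quantities grow with the time a patient is watched, and no test in the list adjusts for it. The false-discovery-rate correction does not help, because the distortion lies inside each comparison and not in the number of comparisons.

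The cohort is retrospective and drawn from routine practice. The lines are defined by treatment history, so nothing in the design equalises observation time between them. If one line is followed for less time, it can look safer than it is, and a true excess in that line can go unseen.

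**Working it through.** **The plan's own figures.** The protocol states no figure for the safety comparison. Its only computed figure, the confidence interval width of 0.28945 for a proportion of 0.5 with n = 50, reproduces as an exact Clopper-Pearson interval (0.35527 to 0.64473). It has no bearing on this point.

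**Inputs from the protocol.** Second, third and fourth line (section 2.2, endpoint 12), 200 expected patients and the named tests (section 4.4), and 24 months as a maximum (section 3.2).

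**Assumed inputs.** AE rate, number of patients per line and observation time per line; the protocol gives none of these. The true rate is set equal in all lines, so a valid 5% test should reject in 5% of trials.

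**Formula.** With a constant rate, P(at least one AE) = 1 − exp(−rate × years). At 0.2 per year, 1.6 years gives 1 − exp(−0.32) = 27.4% and 1.0 year gives 1 − exp(−0.20) = 18.1%. Event counts behave in the same way: the expected counts are 0.2 × 1.6 = 0.32 and 0.2 × 1.0 = 0.20 per patient.

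**Creating a difference.** Simulated rejection rate of the Pearson chi-squared test, three lines of 90/60/50 patients:

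| Observation time by line | Rate per year | Expected % with an AE | Rejects |
|---|---|---|---|
| 24/24/24 months | 0.2 | 33.0 / 33.0 / 33.0 | 5% |
| 22/20/18 months | 0.2 | 30.7 / 28.3 / 25.9 | about 8% |
| 22/20/18 months | 0.5 | 60.0 / 56.5 / 52.8 | about 11% |
| 1.6/1.3/1.0 years | 0.2 | 27.4 / 22.9 / 18.1 | about 17% |
| 1.6/1.3/1.0 years | 0.5 | 55.1 / 47.8 / 39.3 | about 35% |

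With splits of 67/67/66 and 100/60/40 and rates of 0.1 to 0.5 per year, the ranges are 5.5–11% at 22/20/18 months, 10–41% at 20/16/12 months and 17–70% at 24/18/12 months.

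**Masking a difference.** Take 100 patients per group. Group A has a rate of 0.2 over 24 months and group B a rate of 0.4 over 12 months.

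- A: 1 − exp(−0.2 × 2) = 33.0%. B: 1 − exp(−0.4 × 1) = 33.0%.
- The crude test rejects in 5% of trials. If both groups had 24 months, B would show 1 − exp(−0.8) = 55.1% and the test would reject in 89%.
- Over the first 12 months, when both groups are under observation, the figures are 1 − exp(−0.2) = 18.1% against 33.0%. A log-rank test works on that stretch.

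**Choosing the remedy.** Assume identical hazards in every line with early clustering: 1.0 per year for 3 months, then 0.05 per year.

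- Cumulative hazard is 0.25 + 0.05 × 1.35 = 0.3175 by 1.6 years and 0.25 + 0.05 × 0.75 = 0.2875 by 1.0 year.
- Divided by observation time, that is 0.198 against 0.288 per year. The shorter-observed line looks worse although the hazards are the same.
- A constant-rate person-time test then rejects falsely in about 26% of trials (two groups of 100, 1.6 against 1.0 years) and about 18% (three lines of 90/60/50, 1.6/1.3/1.0 years). The log-rank test for time to first AE stays at about 5% in both. The crude test rejects in about 6–7% and 5%.

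**The case against.** The strongest reply is that the protocol never says observation time differs by line. Variation between patients does not bias the comparison; only a systematic difference between lines does. All lines share the same inclusion cut-off (section 3.1), and section 3.1 also limits inclusion to patients with the required data. With modest imbalance (22/20/18 months) the test stays fairly near its nominal level, and with early-clustered events the crude test is hardly disturbed. All of this stands, and it is why the point is conditional.

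Two stronger readings are tempting but not supported:

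- A reader might infer that AEs are to be compared only as crude proportions by chi-squared or exact tests. The sentence refers back to the whole list, including the tests for quantitative data, and the protocol does not fix the AE variable as yes/no. The point survives because none of the listed tests uses observation time.
- A reader might infer that a line in which risankizumab is stopped sooner must look safer. The protocol does not say that AE recording ends when treatment stops. Safety runs over the entire study period, and section 5.1 counts time-points from the start of therapy.

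It can also be said that safety is the last of 13 secondary endpoints, and that a separate analysis plan might add exposure-adjusted rates. The first limits the weight of the point. The second does not answer it, because the protocol itself names the tests for the between-line comparison.

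**Conclusion.** The point holds as a conditional weakness in a stated method. The protocol applies tests that ignore observation time to outcomes that accumulate over it, with follow-up bounded only from above.

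The size depends wholly on how far observation time differs between lines. It is nil with equal observation, small at 22/20/18 months (about 8–11% rejection instead of 5%), and material at 1.6/1.3/1.0 years (about 17–35%). These figures assume constant, equal rates of 20 to 50 first AEs per 100 patient-years and a 90/60/50 split. In the masking case, a doubled rate is lost completely when observation time is halved. A reader might conclude that the planned comparison is certainly biased; the documents do not show that, because they give no observation time by line. The correction is worth making, but it concerns a secondary safety comparison and leaves the primary endpoint untouched.

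**What to change.** In section 4.4, replace the sentence on AEs and SAEs with wording to this effect:

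- Lines are compared by time from start of risankizumab to first AE and to first SAE, using Kaplan-Meier or cumulative incidence curves with a log-rank test or Cox model, censored at last observation.
- Observation time by line and events per 100 patient-years with 95% confidence intervals are reported descriptively.
- Crude counts and percentages are kept as description only.

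This is the framework that section 4.4 already uses for CPDR. A constant-rate Poisson model should not be the main test, since it is biased if AEs cluster early.

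The cost is that AE onset dates must be extracted from the records along with start and last-observation dates, plus slightly more analysis work. The change needs no extra patients or visits. Two limits remain: a first-event analysis ignores repeat events, and it does not remove confounding between lines that were not randomised.
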